---

## LIST OF ABBREVIATIONS

Abbreviation or special term	Explanation
AE	Adverse event
AIS	Acute ischaemic stroke
ASA	Acetylsalicylic acid
BMI	Body mass index
DAE	Premature permanent discontinuation of IP due to adverse event
DMC	Data monitoring committee
FAS	Full analysis set
GUSTO	Bleeding scale: Global Utilization of Streptokinase and Tissue plasminogen activator for Occluded coronary arteries
HR	Hazard ratio
IP	Investigational product
mRS	Modified Rankin scale
NIHSS	National Institute of Health Stroke Scale
SAE	Serious adverse event
TIA	Transient ischaemic attack

## AMENDMENT HISTORY

Date	Brief description of change
09 February 2017	First version published
14 December 2017	1.3 Decimal places added to the significance level
	3.2 Clarification that ischaemic strokes will include strokes classified as “Undetermined” added
	4.1 Reference to the Integrated Quality and Risk Management Plan added
	4.2.1 Decimal places added to the significance level
	4.2.1 Sensitivity analysis updated
	4.2.3 AEs with outcome death added to the safety variables that will be summarised
	5 Decimal places added to significance levels
	5 Critical value added
11 June 2018	1.3 Number of events decreased from 770 to 764, significance level increased from 4.760% to 4.988%, and critical value increased from 0.867 to 0.868, based on updates to the Interim Analysis section
	4.2.1 Significance level updated to 4.988%
	4.2.2 Significance level updated to 4.988%
	4.2.4 Clarifications added regarding the analysis of patients with ipsilateral atherosclerotic stenosis
	5 The p-value at the interim decreased from 0.00762 to 0.001 and Lan-DeMets changed to the Haybittle-Peto procedure. Based on this update, the number of events at the interim have decreased from 462 to 458, the critical value at the interim has decreased from 0.780 to 0.735, and the significance level at the final analysis has increased from 4.760% to 4.988%
	5 A futility analysis has been added
27 May 2019	Signature pages. New study statistician ( ) and global product statistician ( )
	1.2 Number of patients decreased from 13000 to 11000 based on updated study assumptions. Timing of interim analysis changed from 60% to 70% of the primary events
	1.3 Assumed hazard ratio decreased from 0.805 to 0.775 and power increased from 85% to 90%. Based on these changes, the number of events has decreased from 764 to 647, the number of patients has decreased from 13000 to 11000, the significance level has increased from 4.988% to 4.996%, and the critical value has decreased from 0.868 to 0.857

Date	Brief description of change
	3 Rules for handling of data when Visit 3 has occurred outside of the visit window added
	3.3 Clarification regarding patients who never received any dose of IP added
	4.2.1 Significance level updated to 4.996%
	4.2.1 Sensitivity analysis 'on treatment' added
	4.2.1 Rule for handling of data when Visit 4 has been performed outside of the visit window added
	4.2.1.1 Time from index event to loading dose added to subgroup variables
	4.2.2 Significance level updated to 4.996%
	4.2.3 Analyses 'on treatment' added
	4.2.4 Clarification that strokes need to occur prior to or at the date of mRS measurement to be classified as non-disabling/disabling added
	5 Timing of interim analysis changed from 60% to 70% of the primary events. The number of events at the interim has decreased from 458 to 453, the critical value at the interim has decreased from 0.735 to 0.734, and the significance level at the final analysis has increased from 4.988% to 4.996%. The futility limit has decreased from 0.956 to 0.933
09 December 2019	2.1 Definition of safety analysis set and actual treatment added
	3.2 Clarification added to censoring rules in the event of last clinical event assessment occurring later than the date of death
	4.2.4 Added statement that ipsilateral atherosclerotic stenosis $\geq 30\%$ is the main category
	4.2.4 Added peripheral arterial occlusive disease to definition of atherosclerosis in any vascular bed

## **1 STUDY DETAILS**

### **1.1 Study objectives**

#### **1.1.1 Primary objective**

- To demonstrate superior efficacy of ticagrelor and ASA compared with placebo and ASA in AIS/TIA patients in the prevention of the composite of stroke and death at 30 days

#### **1.1.2 Secondary objectives**

- To demonstrate superior efficacy of ticagrelor and ASA compared with placebo and ASA in AIS/TIA patients in the prevention of ischaemic stroke at 30 days
- To demonstrate superior efficacy of ticagrelor and ASA compared with placebo and ASA in AIS/TIA patients in reducing overall disability at 30 days

#### **1.1.3 Safety objective**

- To assess the safety of ticagrelor and ASA compared with that of placebo and ASA in AIS/TIA patients, in particular with respect to major bleeding events

#### **1.1.4 Exploratory objectives**

- To assess the efficacy of ticagrelor and ASA compared with placebo and ASA in AIS/TIA patients with ipsilateral atherosclerotic stenosis in the prevention of stroke and death at 30 days
- To assess the efficacy of ticagrelor and ASA compared with placebo and ASA in AIS/TIA patients in reducing disabling strokes at 30 days
- To describe health-related quality of life in AIS/TIA patients after treating with ticagrelor and ASA or placebo and ASA for 30 days

### **1.2 Study design**

This is a randomised, placebo-controlled, double-blind, parallel-group, international, multicentre Phase III study to test the hypothesis that ticagrelor and acetylsalicylic acid (ASA) is superior to ASA in preventing stroke and death in patients with acute cerebral ischaemia. Patients with acute ischaemic stroke (AIS) or transient ischaemic attack (TIA) before randomisation and who fulfil all of the eligibility criteria will be randomised within 24 hours of symptom onset in a 1:1 ratio to ticagrelor or placebo, with all patients receiving ASA. The study includes 4 visits: on Day 1 (enrolment/randomisation; Visit 1), on Day 5 to 9 (Visit 2), on Day 30 to 34 (end of treatment period; Visit 3), and on Day 60 to 64 (end of study; Visit 4).

A loading dose of 180 mg ticagrelor or placebo will be given on Day 1 as soon as possible after randomisation. Thereafter, patients will receive either ticagrelor 90 mg twice daily or placebo twice daily. All patients should be treated with open-label ASA.

Approximately 11000 patients will be randomised at approximately 450 study sites. The study is event-driven and the final number of randomised patients will be determined based on blind data review. A data monitoring committee (DMC) will conduct an interim analysis for efficacy after approximately 70% of the primary events have been collected.

### **1.3 Number of subjects**

At least 647 primary endpoint events are needed to provide 90% power assuming a hazard ratio (HR) of 0.775 in favour of ticagrelor at the significance level of 4.996%, adjusted for the planned efficacy interim analysis (647 events corresponding to a critical value of 0.857). Based on data from the SOCRATES study, a primary endpoint rate of 6.7% in the placebo group is assumed at 30 days following randomisation. Hence, randomising approximately 11000 patients to ticagrelor or placebo in a 1:1 ratio is expected to yield the 647 events needed. The study is event-driven and the final number of randomised patients will be determined based on blind data review.

## **2 ANALYSIS SETS**

### **2.1 Definition of analysis sets**

All variables, including safety variables, will be analysed using the full analysis set (FAS). All patients who have been randomised to investigational product (IP) will be included in the FAS irrespective of their protocol adherence and continued participation in the study. Patients will be analysed according to their randomised IP irrespective of whether the event occurred before or following discontinuation of IP.

Although the study objectives will be analysed based on the FAS and randomised treatment, a safety analysis set and actual treatment group will be included in the Analysis Data Model datasets. The safety analysis set will include all patients who have received at least 1 dose of randomised IP. Actual treatment will be the treatment actually given irrespective of randomisation. If a patient has received both ticagrelor and placebo, actual treatment group will be the treatment group the patient was randomised to.

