### **2.2 Violations and deviations**

Important protocol deviations will be identified prior to database lock, and will include, but not be limited to:

- Patients who were randomised but did not meet eligibility criteria

- Patients who received prohibited concomitant medication
- Patients who received the wrong IP at any time during the study
- Patients who were randomised but took no IP

Protocol deviations will not imply exclusion from any analyses.

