#### **4.2.3 Analysis of the safety variables**

The time-to-event safety variables will be analysed in the same manner as the primary variable, but will not be included in the confirmatory testing procedure. Sensitivity analyses 'on treatment' will be performed (see Section 4.2.1). Subgroup analyses, as specified in Section 4.2.1.1, will be performed for GUSTO Severe bleeding events. Furthermore, the analysis of GUSTO Severe bleeding events will be repeated with event-free patients censored at Visit 4 (or Day 64) instead of Visit 3 (or Day 34).

SAEs, DAEs, and AEs with outcome death summarised by system organ class and preferred term using the Medical Dictionary for Regulatory Activities, will be presented by treatment group using descriptive statistics.

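### The on-treatment bleeding analyses still group patients by randomised arm, and the safety analysis set as worded leaves out the patients for whom this matters (minor, cheap to mend)

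*SAP*

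**What the plan says.** Section 2.1 sets one rule for the whole plan: "All variables, including safety variables, will be analysed using the full analysis set (FAS"), and "Patients will be analysed according to their randomised IP irrespective of whether the event occurred before or following discontinuation of IP". Section 4.1 repeats the intent-to-treat principle for all analyses.

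Section 2.1 then adds that "a safety analysis set and actual treatment group will be included in the Analysis Data Model datasets", while stating that the objectives will be analysed by randomised treatment. The two items are defined as follows:

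- The safety analysis set: "The safety analysis set will include all patients who have received at least 1 dose of randomised IP".
- The actual treatment group: "Actual treatment will be the treatment actually given irrespective of randomisation", with a rule for mixed exposure: "If a patient has received both ticagrelor and placebo, actual treatment group will be the treatment group the patient was randomised to".

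Section 2.2 lists among the important protocol deviations "Patients who received the wrong IP at any time during the study", and no deviation leads to exclusion.

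For the time-to-event safety variables, Section 4.2.3 adds: "Sensitivity analyses 'on treatment' will be performed (see Section 4.2.1"). The definition in 4.2.1 covers the event window (first dose to last dose plus 7 days), the censoring of event-free patients, and censoring at Day 1 for patients never dosed. It does not mention treatment grouping, so the general rule of 2.1 and 4.1 applies.

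**The concern.** An on-treatment analysis departs from intention to treat so that events can be related to exposure. Here it follows when study product was taken, but not which product. Consider a patient randomised to placebo who received only ticagrelor and had a GUSTO Severe bleed within the window. The plan counts this as an on-treatment placebo bleed, and the reverse error is equally possible.

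Major bleeding is the named focus of the safety objective (Section 1.1.3). Misattribution between arms pulls a harm ratio towards 1, which is the non-conservative direction for safety. The variable that would prevent it is to be derived, but no analysis in Sections 3 to 5 uses it, so no pre-specified analysis shows bleeding by the drug received.

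**Working it through.** No figure in the SAP bears on this point, so there is none to reproduce. The check has two parts.

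**1. Who would be regrouped under the definitions as written?**

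| Product(s) taken | In safety set, read literally? | Actual treatment group |
|---|---|---|
| Randomised product only | Yes | Randomised arm |
| Both products | Yes | Randomised arm (mixed-exposure rule) |
| Wrong product only | No (no dose of randomised IP) | The other arm |
| None | No | Not applicable |

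On the literal reading, actual and randomised treatment agree for everyone in the safety set. Switching to that set by actual treatment would regroup nobody, and would drop the wrong-product-only patients and their bleeds. If the set is read as a dose of any study product, the third row enters and is regrouped. The second row stays in the randomised arm either way.

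The amendment history gives the sequence. The on-treatment safety analyses were added on 27 May 2019. The safety set and actual treatment were added on 09 December 2019, and no change to 4.2.3 is listed for that date.

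**2. How large could the effect be?**

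The SAP gives neither the share of patients with wrong IP nor a bleeding rate, so these inputs are assumptions. Let m be the share of each arm that takes only the other product throughout, and R the true bleeding ratio, ticagrelor to placebo. For rare events, the ratio by randomised arm is approximately

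R_rand = [(1 − m)R + m] / [(1 − m) + mR]

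For R = 3:
- m = 0.5%: 2.99 / 1.01 = 2.96
- m = 1%: 2.98 / 1.02 = 2.92
- m = 2%: 2.96 / 1.04 = 2.85

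Over a wider range:

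| True R | m = 0.1% | m = 0.5% | m = 1% | m = 2% | m = 5% |
|---|---|---|---|---|---|
| 2 | 1.997 | 1.985 | 1.970 | 1.941 | 1.857 |
| 4 | 3.985 | 3.926 | 3.854 | 3.717 | 3.348 |

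For m up to 1% and R up to 4 the ratio falls by less than 4% (3.854 / 4 = 0.964). At m = 5% it falls by about 7% for R = 2 (1.857 / 2 = 0.929) and 16% for R = 4 (3.348 / 4 = 0.837).

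In events, take 5500 patients per arm (11000 randomised 1:1, Section 1.3), an assumed placebo bleeding risk of 0.2%, R = 4 and m = 1%:
- ticagrelor-exposed bleeds counted under placebo: 5500 × 0.01 × 0.002 × 4 = 0.44
- placebo-exposed bleeds counted under ticagrelor: 5500 × 0.01 × 0.002 = 0.11

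With sparse events a single case is visible. If the counts by drug taken were 16 and 4 (ratio 4.0), moving one ticagrelor bleed to placebo gives 15 and 5 (ratio 3.0).

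**The case against.** The strongest reply is that this is a choice and not a mistake. Section 2.1 says openly that objectives are analysed as randomised and that the extra variables are only carried in the datasets. Section 4.2.1 defines on-treatment as a time window and does not claim to be an as-treated analysis. That stands: a reader might infer that the SAP contradicts itself or that its main safety analysis is invalid, and the text supports neither.

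A second reply is that the effect is negligible. In the sparse example a patient who took only the wrong product must also have bled. Even then the shift, log(4/3) = 0.29, is about half a standard error, √(1/16 + 1/4) = 0.56, and the approximate 95% interval around 4.0 runs from 1.3 to 12.0. Section 2.2 lists wrong IP at any time without a frequency, and some of those patients will have taken both products. This also stands, and it limits the severity.

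A reader might also infer that never-dosed patients dilute the on-treatment contrast. They do not add event-free follow-up to it, because 4.2.1 censors them at Day 1; Section 3.3 does the same for discontinuation due to bleeding. They do remain in the denominators of the SAE and DAE tables. Those tables are descriptive, and for DAEs a similar never-dosed share in both arms lowers both percentages by the same factor and leaves their ratio unchanged.

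Finally, wrong-IP patients are identified before database lock and the variable will exist, so a supplementary look remains possible. But none is pre-specified, and with the safety set as worded it could omit the patients of interest.

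**Conclusion.** The point holds as a low-severity improvement. The on-treatment bleeding analyses follow exposure in time but not by product, the actual treatment group is used in no planned analysis, and the safety analysis set read literally excludes the patients whose actual treatment differs from the randomised one. The first two follow directly from the text. The third depends on taking the words randomised IP at face value; the sponsor may simply have meant study product.

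The direction of bias is towards no difference, provided that wrong-product exposure occurs in both arms and ticagrelor raises bleeding. Its size is unknown because the SAP gives no rate. Under the assumed shares of 0.5% to 2%, a true ratio of 3 would be reported as 2.96 to 2.85. Nothing in the document shows that a safety conclusion would change, and the randomised full-analysis-set comparison remains sound as the main safety analysis.

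**What to change.** - **Main analyses:** keep the full-analysis-set safety analyses by randomised arm.
- **Section 2.1:** define the safety analysis set as patients with at least one dose of any study IP, whichever product it was.
- **Section 4.2.3:** state that the on-treatment analyses of GUSTO Severe bleeding, intracranial haemorrhage or fatal bleeding, and GUSTO Moderate/Severe bleeding use that set, grouped by actual treatment.
- **Mixed exposure:** list bleeds in patients who received both products, with the product being taken at onset, since regrouping does not reach them.
- **Optional:** repeat the descriptive SAE, DAE and fatal-AE tables on the reworded safety set by actual treatment.

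The cost is a few lines of SAP text, one listing, and on-treatment outputs run with variables that are already to be derived. The downside is that the on-treatment safety comparison is no longer strictly as randomised; the main analysis still provides that comparison.

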### **2.2 Violations and deviations**

Important protocol deviations will be identified prior to database lock, and will include, but not be limited to:

- Patients who were randomised but did not meet eligibility criteria

- Patients who received prohibited concomitant medication
- Patients who received the wrong IP at any time during the study
- Patients who were randomised but took no IP

Protocol deviations will not imply exclusion from any analyses.

### **3 PRIMARY AND SECONDARY VARIABLES**

#### **3.1 Primary variable**

The primary variable is the time from randomisation to first subsequent stroke or death. Patients who have not experienced either of these events will be censored at Visit 3, Day 34, or the date of last event assessment, whichever occurs earlier. If Visit 3 has occurred within the visit window, Day 30 to 34, events will be included up to the date of Visit 3 (inclusive). If Visit 3 has occurred outside of the visit window (or is missing), it will be replaced by Day 34 for event inclusion and censoring.

Time will be calculated as the number of days plus one between the date of randomisation and the date of the first occurrence of the event, or, if no event has occurred, the date of censoring.

#### **3.2 Secondary variables**

The secondary variables, presented in the hierarchical order in which they will be tested, are:

- 1 Time from randomisation to first subsequent ischaemic stroke (including strokes classified as “Undetermined”)
- 2 mRS score >1 at Visit 3

For the time-to-event variable, patients who have not experienced the event will be censored at Visit 3, Day 34, or the date of last event assessment, whichever occurs earlier. If Visit 3 has occurred outside of the visit window (or is missing), see Section 3.1. Furthermore, if the last clinical event assessment has occurred later than the date of death, the date of death will be used as the date of last clinical event assessment (applicable for all time-to-event variables not including death).

The mRS score for patients who have died prior to Visit 3 will by definition be 6. No other imputation for missing data will be made. However, if Visit 3 has occurred prior to Day 30 and the patient has died prior to or at Day 34, the mRS score will be 6.

#### **3.3 Safety variables**

The safety variables are:

- Time from randomisation to first bleeding event that fulfils SAE criteria and is categorised as GUSTO Severe
- Time from randomisation to first intracranial haemorrhage or fatal bleeding event
- Time from randomisation to first bleeding event that fulfils SAE criteria and is categorised as GUSTO Moderate/Severe
- Time from randomisation to premature permanent discontinuation of IP due to bleeding
- Occurrence of SAE
- Occurrence of DAE

For the time-to-event variables, patients who have not experienced the event will be censored at Visit 3, Day 34, or the date of last event assessment, whichever occurs earlier; or, for the time from randomisation to discontinuation due to bleeding variable only, the day of the last dose of IP, if earlier. Patients who never received any dose of IP will be censored at Day 1 for the discontinuation due to bleeding variable. If Visit 3 has occurred outside the visit window (or is missing), see Section 3.1.

### **3.4 Exploratory variables**

The exploratory variables are:

- Time from randomisation to first subsequent stroke or death in patients with ipsilateral atherosclerotic stenosis
- mRS score >2 at Visit 3 in patients with subsequent stroke
- EQ-5D-5L profile

For the time-to-event variable, patients who have not experienced the event will be censored at Visit 3, Day 34, or the date of last event assessment, whichever occurs earlier. If Visit 3 has occurred outside the visit window (or is missing), see Section 3.1.

The mRS score for patients who have died prior to Visit 3 will by definition be 6. If Visit 3 has occurred prior to Day 30 and the patient has died prior to or at Day 34, the mRS score will be 6. Furthermore, for the disabling stroke variable (mRS score >2 at Visit 3 in patients with subsequent stroke), the stroke must have occurred prior to or at the date of the mRS measurement.

## **4 ANALYSIS METHODS**

### **4.1 General principles**

All analyses will be based on the intent-to-treat principle, using the FAS. In time-to-event analyses, the treatment groups will be compared using a Cox proportional hazards model with a factor for treatment group, using the Efron method for ties. P-values and 95% confidence

intervals for the HR will be based on the Wald statistic. In summary tables of these analyses, in addition to HR with confidence intervals and p-values, presentations will include the number and percentage of patients with events and Kaplan-Meier estimates of the event rate per treatment group. Kaplan-Meier estimates of the cumulative proportion of patients with events will be calculated and plotted, with the number of patients at risk indicated below the plot at specific time points. If the total number of events is less than 15, only the number and percentage of patients with events will be presented, but no Kaplan-Meier estimates, HRs, confidence intervals, or p-values.

No multiplicity adjustment will be made to confidence intervals as they will be interpreted descriptively and used as a measure of precision. The primary variable and the secondary variables will be included in a confirmatory testing procedure.

Continuous variables will be summarised by treatment group using descriptive statistics, including the number of patients, mean, standard deviation, median, and range as appropriate. For categorical variables, counts and percentage per treatment group will be presented.

For a description of the critical to quality factors, and processes to ensure the quality of study conduct and the validity of study results, see the Integrated Quality and Risk Management Plan.

